##### **5.9.6.1. Unblinding**

Emergency unblinding of the treatment assignment for a patient may be necessary due to a medical emergency, a serious adverse event (SAE) that is unexpected and for which a causal

relationship to IMP cannot be ruled out, or any other significant medical event (e.g., pregnancy).

If unblinding is required for a medical emergency:

- Only the investigator will make the decision to unblind the treatment assignment.
- Only the affected patient will be unblinded.
- An emergency envelope will provide the treatment assignment to the investigator.

The investigator will notify the sponsor and/or designee immediately that the patient has been unblinded.

Emergency unblinding will be done by sealed unblinding envelopes. The envelopes will be prepared centrally by IMSB and sealed by the study pharmacists. Study pharmacists receive a request for a specific patient ID and randomise the patient using his or her patient ID via ALEA 17.1. The study pharmacists then write the patient ID on a prepared letter that contains the randomized treatment for this patient and seal the letter so that the patient ID can be seen in the window of the envelope.

Data will be unblinded after the last participant has completed the visit planned for day 7 after trial drug administration for a first data analysis of the expansion cohort (**Group 2D**). Unblinding is done by the IMSB. Results are not communicated to participants during the trial and are used to inform the further development of DZIF-10c.

#### **5.9.7. Previous and Concomitant Medication**

Following trial drug administration, the standard of care may be provided as required by the medical condition and deemed appropriate by health care providers.

#### **5.9.8. Rescue Therapy for Emergencies**

All trial sites are embedded into a maximum-care hospital facility capable of providing immediate emergency therapy including specialized medical intensive care.

No specific rescue therapy for DZIF-10c is available. In case of an acute infusion reaction, the infusion will be interrupted and not be re-initiated. For infusion reactions requiring medical intervention, rescue medication including, but not limited to, acetaminophen/paracetamol, antihistamines, glucocorticoids, and IV fluids must be available on-site. In case of bronchial hyperresponsiveness (e.g., bronchospasm), bronchodilators and antiinflammatory medication may be provided by inhalation or intravenously as deemed clinically appropriate.

### **5.9.9. Continuation of Treatment after the End of the Clinical Trial**

Study participants will receive no additional administrations of DZIF-10c beyond the planned administration as per group assignment.

## **6. Data Quality Assurance**

### **6.1. Monitoring and Audits**

#### **6.1.1. Monitoring**

Regularly scheduled monitoring will be performed by the Clinical Trials Center Cologne (CTCC) Monitoring team at all trial sites. This monitoring process aims to ensure the study participants' safety, that data is collected accurately and completely, that the clinical trial is conducted according to the trial protocol, and that all principles of GCP and applicable guidance are followed.

A monitoring plan will define the specific extent of the monitoring procedures for all sites. All Principal Investigators will agree to regularly performed monitoring and provide appropriate support to the delegate of the CTCC Monitoring team to fully conduct the monitoring procedures and ensure access to all relevant trial-related documentation including source documents. Monitoring procedures will additionally include drug accountability checks at the local study pharmacies to ensure accurate documentation and handling of study drug, as well as monitoring of local study research laboratories to ensure proper sample handling and storage.

Each monitoring visit will be followed by a written visit report summarizing the visit and any potential findings.

#### **6.1.2. Audits / Inspections**

For purposes of quality assurance, the sponsor or a delegate assigned by the sponsor will have the right to audit trial sites and other institutions involved in this clinical trial. The objectives of such audits include the ensurance of trial participants' safety, and the verification of data accuracy, validity, and completeness. To perform these tasks, auditors will receive access to all relevant trial documentation including source documentation, drug accountability documentation, and any trial-related correspondence.

Inspections may be performed by competent authorities as indicated by applicable law and guidelines.

The sponsor and all trial sites will commit to support auditors and inspectors of competent authorities at all times, and to provide all necessary original documentation.

## 6.2. Documentation

Principal Investigators will oversee and coordinate data collection, entry, and protection. Trial-specific data will be collected by the clinical trial staff using designated source documents. Standard GCP practices will be followed to ensure accurate, reliable and consistent data collection. Any correction to source documentation needs to ensure a valid correction trail, including leaving original entries legible and signed or initialed dated corrections.

All trial data must be verifiable to the source documentation. All source documents will be kept in a locked facility at the clinical site. Source documents include but are not limited to

- Informed Consent Forms
- Reported laboratory results
- Lists of adverse events
- Lists of concomitant medication
- Documentations of existing conditions.

Medical records will be archived by the Medical Record Department of the hospital.

All data relevant to the trial are documented by the Principal Investigators (PI) or designees in corresponding electronic case report forms (eCRFs). All eCRFs and laboratory reports will be reviewed by the clinical team to ensure that they are accurate and complete.

The Principal Investigators may authorize trial staff members to sign the eCRFs to confirm accuracy of the data. At the completion of the follow-up visits, final sign-off must be performed by the Principal Investigators.

### 6.2.1. Data Management

The IT infrastructure and dedicated staff will be provided by the Clinical Trials Center Cologne (CTCC, ZKS Köln). A trial-specific database will be developed and validated prior to data entry based on standard operating procedures established at the CTCC. The data management system is based on commercial, validated trial software.

All changes to data stored within the trial database will be documented in an audit trail. The trial software has a user and role concept that can be adjusted on a trial-specific basis. Access to the trial database is restricted, and the database is embedded into an IT infrastructure with a dedicated safety concept including a firewall and backup systems. Data within the trial database are backed up daily.

Data will be entered online at the local trial sites via the internet. During data entry, automated plausibility checks will be performed, thereby detecting many discrepancies immediately. CTCC staff will conduct additional checks for data completeness and plausibility and clarify any questions with the local trial staff using an electronic query system of the trial software.

These electronic queries have to be answered by the trial site without unreasonable delay. Further details will be specified in the data management plan.

eCRF Completion Requirements will be provided to the trial sites for detailed descriptions of the respective procedures.

After completion or termination of the clinical trial and data cleaning, the database will be locked and the data exported for statistical analysis.

### **6.2.2. Archiving**

All essential trial documents including investigator and sponsor parts of the TMF will be archived for 15 years according to ICH-GCP (Chapter 8).

The trial master file, the eCRFs, the code envelopes and other material supplied for the performance will be archived according to applicable regulations and laws.

## **7. Ethical and Regulatory Aspects**

### **7.1. Ethics Committee**

A favorable opinion by the competent ethics committee will be obtained before initiating any trial procedures.

### **7.2. Ethical and Legal considerations**

This trial will be conducted in agreement with the principles of the Declaration of Helsinki as well as the Good Clinical Practice guidelines by the International Council for Harmonisation of Technical Requirements for Registration of Pharmaceuticals for Human Use (ICH-GCP), and all applicable law.

### **7.3. Registration and Notification of Authorities**

This clinical trial has been registered at the EU Clinical Trials Register (EudraCT: 2020-004448-27) and at ClinicalTrials.gov (NCT04631705).

Prior to study initiation, approval will be obtained from the federal competent authority (Paul-Ehrlich-Institute), and state and local authorities will be notified as per applicable regulations.

### **7.4. Obtaining Informed Consent from Trial Participants**

Prior to the initiation of any clinical trial-related procedures, potential trial participants will be provided with a copy of the most recent informed consent form approved by the local ethics committee to read. In addition, the Principal Investigator or a Subinvestigator will discuss the specifics of the clinical trial with the potential participants verbally. This discussion will include but not be limited to the purpose for conducting the clinical trial, the procedures to be conducted, the time commitment required by the participant, the drug and placebo to be administered, potential benefits and risks of participation, alternative options for treatment, patient confidentiality, and potential access to data by representatives of the sponsor (e.g., monitors or auditors) and competent authorities. As part of this discussion, potential participants will be informed that participation in the clinical trial is completely voluntary, and that withdrawal of consent is possible at any time without the need to provide reasons and will not jeopardize the participant's future medical treatment. The informed consent discussion will be led in a comprehensible manner using language that is readily understandable by the potential participant.

Potential participants will be given the opportunity to ask questions to the investigators and express potential concerns, and to discuss potential participation in the clinical trial with family, friends, and/or other health care providers.

Originals of the signed informed consent forms will be stored in the investigator site file, and trial participants will be provided with a copy of the participant information sheet and the signed informed consent form. Receipt of this copy will be confirmed by the participants by signature on the informed consent form.

### **7.5. Insurance of Trial Subjects**

All study participants will be provided insurance in accordance with § 40 AMG. The insurer's name, contact details, and policy number will be provided in the participant's information sheet.

### **7.6. Data Protection**

All investigational materials and data will be pseudonymized using unique alphanumerical codes for each trial participant, and all applicable provision of the data protection legislation will be followed. As part of the informed consent process, potential trial participants will be informed about the requirement to agree to handling of pseudonymized data in accordance with applicable legislation to be eligible to participate in the trial.

The sponsor (University of Cologne) is responsible for data processing (University of Cologne, [name], Data Protection Officer: Phone: [REDACTED], Fax: [REDACTED], E-Mail: [REDACTED]). In this trial, the sponsor is represented by [REDACTED] [REDACTED]. Data processing will be carried out by the Clinical Trials Centre Cologne at the University of Cologne (CTCC, [name]).

## 8. Statistical Methods and Sample Size Considerations

### 8.1. Statistical and Analytical Plan

For each study phase (dose escalation and randomized) a first analysis is planned after the data from up to the day 7 visit after administration of the study drug is collected and data is cleaned. In the expansion cohort (**Group 2D**), data will be unblinded for this analysis. The final analysis will take place after the follow up for all subjects of both phases is completed. The final CTR will include all study phases.

In group 2D, no adjustments for dropouts are planned.

#### 8.1.1. Analysis Populations

##### Dose-Escalation Phase (Groups 1A-1C and Groups 2A-2C)

Analyses are conducted “as treated”, which includes all participants who received any amount of the study drug.

##### Randomized Placebo-Controlled Phase (Group 2D)

The primary dataset for analysis is the safety population (as treated). This population includes all trial subjects who received any amount of the study drug.

The secondary dataset for analysis is a modified intention-to-treat (mITT) population. This dataset includes all randomized trial participants receiving study drug inhalation and infusion and who have at least a baseline (day 0) value and a second measurement of viral RNA shedding in nasopharyngeal swabs by qRT-PCR up to the day 7 visit. The evaluation is carried out strictly in accordance with the allocation by randomization.

Additional analysis populations can be defined in the SAP.

#### 8.1.2. Description of Trial Participants Groups

Quantitative data will be summarized by mean  $\pm$  standard deviation and percentiles (0, 25, 50, 75, 100). Qualitative data will be summarized by absolute and relative frequency. Confidence intervals can support interpretation, if sensible. Listings of the data will be given where appropriate. Data up to the day 7 visit after administration of the study drug and during follow up will be evaluated separately and in aggregate as appropriate.

### **Dose-Escalation Phase (Groups 1A-1C and Group 2A-2C)**

Descriptions will be provided by DZIF-10c dose and infection status, as well as in aggregate. Listings of the data by participant will be provided for all safety data.

### **Randomized Placebo-Controlled Phase (Group 2D)**

Descriptions will be provided by treatment group and in aggregate. Listings of the data by participant will be provided for all safety data.

### **Screening failures**

Screening failures will be listed with available information on demography, the cause for the screen failure and Adverse Events.

#### **8.1.3. Primary Outcome and Target Variables**

Primary target variables are Adverse Events (including Serious Adverse Events and Adverse Events of Special Interest), as defined in chapter 5.2.1 and chapter 9. Evaluation will be performed in the safety population. Safety events will be listed by participant. Safety events are reported in total, by seriousness, relatedness, and severity.

Analysis is descriptive. Safety events will be evaluated as rate and frequency of participants who experienced the event and also as number of events.

Safety events will be evaluated in the time period until the day 7 visit after trial drug administration, after the day 7 visit until the end of study, and in aggregate. An exception are AESIs, which will be documented as AESIs until the day 7 visit only.

#### **8.1.4. Secondary and Exploratory Outcomes and Target Variables**

Analysis is descriptive in nature. Secondary and exploratory endpoints will be evaluated by dose or treatment group and visit. Endpoints will be evaluated mainly in the safety population (dose escalation phase) or in the mITT population (**Group 2D**). Figures may show development over time where sensible. Endpoints can additionally be analysed by suitable multivariable models, including covariates. Substitution of missing values is not planned; the main efficacy analysis of time weighted average change of viral RNA shedding is possible in the mITT without substitutions. Complete methods will be specified in the SAP.

## Outcomes and Target Variables

### Laboratory Parameters, Vital Signs, Symptoms

Changes in safety laboratory parameters, vital signs and symptoms will be summarized descriptively. Changes in laboratory parameters and vital signs will additionally be calculated relative to the results obtained at baseline (day 0 prior to study drug administration).

### Pharmacokinetic Parameters

Pharmacokinetic parameters of DZIF-10c in antibody recipients will be calculated using standard non-compartmental analysis. The complete methodology will be defined in the Statistical Analysis Plan.

### Anti-Drug Antibodies

The frequency of participants with antibodies and magnitude (i.e., titer) of antibodies targeting DZIF-10c will be calculated and described in tables.

### Viral Shedding Determined by qRT-PCR

Viral RNA shedding in nasopharyngeal and oropharyngeal swabs will be measured by qRT-PCR as Ct values and copies/ml. Viral RNA shedding will be evaluated as original values and difference to baseline by visit, and as time weighted average change between baseline and the day 7 visit, as well as between baseline and the day 14 visit (**Groups 2A-2D**). In addition, the proportion of SARS-CoV-2-RNA positive participants per group and swab type will be determined (**Groups 2A-2D**).

### Viral Shedding Determined by the Isolation of Infectious Virus

Frequency of viral shedding as determined by successful isolation of infectious virus in virus isolation assays will be analysed by visit (**Groups 2A-2D**).

### Viral Replication Determined by Subgenomic SARS-CoV-2 mRNA

Levels of subgenomic SARS-CoV-2 mRNA will be determined in swab samples by qRT-PCR and summarized (**Groups 2A-2D**).

### Frequency of COVID-19-related hospitalizations and medically-attended contacts

The frequency of unplanned hospitalizations and medically-attended contacts deemed to be related to COVID-19 by the Investigator will be described (**Groups 2A-2D**).

#### Time to symptom resolution

The duration of COVID-19-related symptoms will be described based on participants's self-assessment documented on patient diaries (**Groups 2A-2D**).

#### Differences in Viral Sequences and Change in Neutralization Sensitivity

Sequencing results of SARS-CoV-2 spike genes will be described. The impact of individual mutations (e.g., within the antibody epitope or recurrent mutations) on DZIF-10c sensitivity will be determined by neutralization assays and 50% inhibitory concentrations ( $IC_{50}s$ ) and/or 100% inhibitory concentrations ( $IC_{100}s$ ) will be determined (**Groups 2A-2D**).

#### Activity and Frequency of SARS-CoV-2-reactive immune responses

The frequency and response magnitude of SARS-CoV-2-reactive lymphocytes or lymphocyte subset will be evaluated and summarized per participant (**Groups 2A-2D**).

#### **8.1.5. Subgroup Analyses**

All subgroup analyses will be descriptive only. A subgroup analyses for sex will be performed for the primary endpoint.

Additional subgroup analyses are planned in the expansion cohort (**Group 2D**) for age, sex, BMI, viral RNA shedding at baseline, and trial center. The definition of Subgroup categories and minimum number of participants for a subgroup analysis will be specified in the SAP.

#### **8.1.6. Interim Analysis**

No formal interim analysis is planned.

### **8.2. Sample Size Considerations**

During the dose escalation phase of the trial, a routine 3+3 trial design will be employed.

Since this is a hypothesis-generating trial, no formal sample size calculation is done for the randomized expansion study part. Selection of the group size included considerations of feasibility for an early phase first-in-human trial in quarantined individuals while facilitating outcome measures that can inform later stage trials. 60 participants will be included in the

expansion cohort with 20 participants per arm. Assuming a similar rate of participants experiencing Adverse Events as observed in a previous clinical trial of a SARS-CoV-2-neutralizing antibody in ambulatory SARS-CoV-2-infected participants, the following confidence intervals for the rate of Adverse Events in the expansion cohort can be calculated per group of 20 participants:

Rate of AEs (Participants)	90% confidence interval (Participants with AEs)
20%	[5% ; 35%]
25%	[9% ; 41%]
30%	[13% ; 47%]

While this exploratory trial is not powered to determine statistically significant differences in the change of the viral load between the treatment arms in the expansion cohort, simulations based on effects observed for previously reported SARS-CoV-2 neutralizing antibody responses indicate that an AUC ratio  $>1.45$  between a treatment arm of with a similar effects and controls can be observed with  $>80\%$  probability at a group size of 20.

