#### **5.9.4. Assignment of Trial Participants to Treatment Groups**

In the expansion cohort (**Group 2D**) participants are randomized 1:1:1 (placebo only:DZIF-10c inhalation and placebo i.v.:DZIF-10c inhalation and DZIF-10c i.v.) into the trial groups without stratification. Randomization will be implemented by a 24/7-Internet service (ALEA 17.1, FormsVision BV, Abcoude, NL) and prepared centrally by the Institute of Medical Statistics and Computational Biology (IMSB) at the University of Cologne.

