7.4.1 Primary analysis of the primary endpoint

The primary endpoint analysis, implemented separately for phase I and phase IIa, will evaluate the proportion of patients with any adverse event occurring within 7 days of study drug administration.

As this study is exploratory and hypothesis generating in nature, no formal statistical testing will be implemented. Handling of missing data points is described in [Section 6.6.1](#). Please note that the number of events will also be provided in listings. All adverse events with onset during the first 7 days after drug administration will be taken into consideration for this endpoint analysis, and an overall summary of AE occurrences (N and %) will be created. In addition to the occurrence of adverse events the following AE attributes will be presented and evaluated:

- Severity / Maximum CTCAE grade
- Relatedness
- Outcome
- Time to first occurrence [days]

As one specific aim of the study is to determine a safe dose to be taken forward into subsequent development, the evaluation of dose-limiting toxicities (DLT) is of particular importance in the phase I part of the trial. A DLT for this trial will be defined as any grade 3 or higher adverse event that the investigators determine to be related to DZIF-10c. The following evaluations will therefore be implemented:

- Proportion of patients with DLTs after DZIF-10c inhalation occurring within 7 days of study drug administration.

Any AE meeting the criteria for DLT, regardless at which point in time after drug administration it occurred, will be considered a significant adverse event (SIAE). The analysis of non-serious SIAEs and serious adverse events (SAEs) is described in [Section 7.8.1](#) of this document.

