In addition to a time-weighted average change, changes from baseline will also be evaluated using a restricted maximum likelihood (REML) based repeated measures approach. Analyses will include the fixed, categorical effects of antibody status, and treatment-by-visit interaction, as well as the continuous, fixed covariates of baseline and baseline-by-visit interaction. An unstructured (co)variance structure will be used to model the within-subject measurements. In

case the model does not converge, other covariance structures will be used sequentially until convergences is reached and the used covariance structure will be reported. The sequence of covariance structures to be used is as follows: unstructured, antedependence, heterogeneous Toeplitz, Toeplitz, heterogeneous AR(1). The Kenward-Roger approximation will be used to estimate denominator degrees of freedom.

All model-based evaluations (time-weighted average change and MMRM) will be done for the following time periods:

- first 7 days after drug administration
- first 14 days after drug administration
- first 28 days after drug administration

Note that only data points within the analysis periods are considered. Data available after the cut-offs will not be considered for the model based evaluations.

All model-based evaluation will be done for the SARS-CoV-2 E gene. As sensitivity analyses, the evaluations will be repeated for the additionally assessed SARS-CoV-2 gene (ORF1a/b gene). This sensitivity analysis will be done on subjects from the subject set TS who have at least a baseline value and a second measurement in the respective time period of viral RNA shedding in OP swabs by qRT-PCR.

Clearance rate

It will be shown how many patients fell below the limit of valid quantification. Finally, the proportions of participants with positive and negative PCR for each assessed SARS-CoV-2 gene assessed at every given visit will be described (clearance rate). Missing data will not be imputed. Consequently, the number of patients with non-missing data will be used as denominator for each proportion. CIs for the proportions will be derived as Clopper-Pearson intervals.

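### The 90% intervals for AE rates in Protocol 8.2 are unnamed Wald intervals, with upper limits 3.9 to 5.4 points below the exact (Clopper-Pearson) ones, and SAP 7.4.1 plans no interval for the primary AE proportion

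*Protocol*

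**What the plan says.** Protocol 8.2 plans an "expansion cohort with 20 participants per arm" and states that "no formal sample size calculation is done for the randomized expansion study part". It gives feasibility in quarantined participants, and the wish for outcome measures that can inform later trials, as considerations for the group size. It then says that "the following confidence intervals for the rate of Adverse Events in the expansion cohort can be calculated per group of 20 participants", and tabulates a "90% confidence interval" for three assumed AE rates: 5-35% at 20%, 9-41% at 25% and 13-47% at 30%. The interval method is not named. Protocol 8.1.2 allows confidence intervals as an aid to interpretation but does not require them.

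SAP 5.1 and 7.4.1 define the primary endpoint as the proportion of patients with any AE within 7 days of study drug. For its analysis, SAP 7.4.1 says that "an overall summary of AE occurrences (N and %) will be created". Severity, relatedness, outcome, time to first occurrence and listings are added, and there is no formal test. Neither 7.4.1, 7.4.2 nor 7.8.1 specifies a confidence interval for this proportion.

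Elsewhere the SAP does plan intervals. For PCR clearance (SAP 7.5.2.2.3), "CIs for the proportions will be derived as Clopper-Pearson intervals". The example code in SAP 9.2.3 requests exact binomial limits for hospitalisation or medical contacts and for PCR status by visit. Confidence intervals are also planned for the viral-load means and ratios (7.5.2.2.3) and for the symptom hazard ratios (7.6.2.5).

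**The concern.** With 20 participants and rates of 20-30%, a Wald interval is symmetric around the estimate although the binomial distribution is skewed. Both of its limits sit too low, and it can cover less often than its label says. For an AE rate, the low upper limit is the optimistic side. A reader of Protocol 8.2 would take 20 per arm to exclude AE rates that a better interval does not exclude.

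There is also a mismatch between the two documents. The protocol describes what the expansion cohort can say about AE rates as an interval. The SAP, which should carry that into the analysis, gives the primary proportion no interval, while secondary and exploratory proportions get exact ones. What is at stake is how honestly precision is presented, before the trial and in the report. No design or dosing decision depends on it.

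**Working it through.** **Inputs.** From Protocol 8.2: n = 20 per arm, a 90% two-sided level (z = 1.645), and assumed rates of 20%, 25% and 30%, which correspond to 4, 5 and 6 of 20. The comparator is Clopper-Pearson, which the SAP names in 7.5.2.2.3. Wilson is added as a less conservative check.

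**Step 1: reproduce the table.** Wald: p ± 1.645 × √(p(1−p)/20).

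- 20%: 1.645 × √(0.20 × 0.80/20) = 0.147, giving 5.3-34.7%
- 25%: 1.645 × √(0.25 × 0.75/20) = 0.159, giving 9.1-40.9%
- 30%: 1.645 × √(0.30 × 0.70/20) = 0.169, giving 13.1-46.9%

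Rounded, all six limits match the protocol. At 90%, continuity-corrected Wald, Clopper-Pearson, Wilson, Agresti-Coull, Jeffreys and mid-P do not reproduce the table. Wald at 95% does not either.

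**Step 2: compare with other intervals.** For x events, the Clopper-Pearson limits are the 5th percentile of Beta(x, 21−x) and the 95th percentile of Beta(x+1, 20−x).

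| Events | Wald 90% | Clopper-Pearson 90% | Upper-limit gap | Wilson 90% | Upper-limit gap |
|---|---|---|---|---|---|
| 4/20 | 5.3-34.7 | 7.1-40.1 | 5.4 | 9.3-37.8 | 3.1 |
| 5/20 | 9.1-40.9 | 10.4-45.6 | 4.6 | 12.7-43.2 | 2.3 |
| 6/20 | 13.1-46.9 | 14.0-50.8 | 3.9 | 16.4-48.4 | 1.5 |

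Limits are in %, gaps in percentage points from unrounded limits. The Wald lower limits are also below the Clopper-Pearson ones, by 1.9, 1.3 and 0.8 points. Total width rises from 29.4, 31.9 and 33.7 points (Wald) to 33.0, 35.2 and 36.8 points (Clopper-Pearson).

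**Step 3: actual coverage.** For each true rate, add the binomial(20, p) probabilities of the event counts whose interval contains p.

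| True rate | Counts whose Wald interval covers | Wald coverage | Chance Wald upper limit is below the true rate | Clopper-Pearson coverage | Same chance, Clopper-Pearson |
|---|---|---|---|---|---|
| 20% | 2-7 | 89.9% | 6.9% (0-1 events) | 95.6% | 1.2% |
| 25% | 3-8 | 86.8% | 9.1% (0-2 events) | 93.5% | 2.4% |
| 30% | 4-9 | 84.5% | 10.7% (0-3 events) | 91.7% | 3.6% |

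The nominal values are 90% for coverage and 5% for each tail. At 20% the two-sided Wald coverage is essentially nominal, but only because a short lower tail (3.2%) offsets the long upper one (6.9%).

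**Step 4: precision of an arm contrast, if one were reported.** With equal rates and 20 per arm, the approximate 90% half-width is 1.645 × √(2p(1−p)/20). This gives 20.8, 22.5 and 23.8 points at 20%, 25% and 30%. Such a contrast would be very imprecise.

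**The case against.** A good deal of the opposing case stands.

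- **It is a choice of method.** A reader might infer a calculation error. There is none: the table is correct as a set of Wald intervals.
- **The sample size does not rest on it.** A reader might infer that weaker precision undermines 20 per arm. Protocol 8.2 disclaims a formal calculation, cites feasibility, sets no precision target and adds a separate viral-load statement. Replacing 5-35% with 7-40% changes no group size.
- **The comparator matters.** Clopper-Pearson over-covers here (91.7-95.6%), so part of the 3.9 to 5.4 points is its conservatism. At a true rate of 20%, Wilson covers only 84.4%, so Wald is not the worst two-sided interval in every row. The upper limits are nevertheless low against Wilson too.
- **The SAP names Clopper-Pearson for PCR clearance and codes exact limits for a few other proportions, not for AEs.** The protocol table therefore contradicts no stated AE method.
- **No decision uses the upper limit.** Escalation and halting follow DLT counts and related grade 3 or higher or serious events (Protocol 3.4 and 4.1.1), not a bound on the any-AE rate.
- **The data will be visible.** A reader might infer that information on precision will be lost. SAP 7.8.1 tabulates AEs by treatment, so an interval can be computed from the reported counts, and Protocol 8.1.2 permits one.

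The descriptive character of the analysis is the weakest objection. An interval labelled descriptive involves no test, and the SAP already gives intervals to other exploratory results.

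**Conclusion.** The point holds as one of method and reporting. The table in Protocol 8.2 uses an unnamed Wald interval whose upper limits are 5.4, 4.6 and 3.9 points below Clopper-Pearson and 3.1, 2.3 and 1.5 points below Wilson. At the tabulated rates the nominal 90% coverage is in fact 84.5-89.9%, and the upper limit misses the true rate 6.9-10.7% of the time instead of 5%. SAP 7.4.1 leaves the primary AE proportion without any interval. That is a gap in specification and not a prohibition.

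These figures assume 20 evaluable participants in each arm, as planned ("participants are randomized 1:1:1"; "In group 2D, no adjustments for dropouts are planned"), and independent binomial outcomes. Fewer treated participants would widen every interval. The documents do not support a claim that the group size is wrong, that the table contains an arithmetic error, or that safety oversight is impaired.

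**What to change.** 1. In Protocol 8.2, replace the three intervals with exact ones, 7-40%, 10-46% and 14-51%, and state that they are 90% Clopper-Pearson intervals.
2. In SAP 7.4.1, add a Clopper-Pearson interval per arm for the proportion with any AE within 7 days, labelled descriptive. State the confidence level; 90% would match Protocol 8.2. The exact-binomial code in SAP 9.2.3 can be reused with the level set explicitly, because the example sets none.
3. Optional: add a descriptive risk difference of each DZIF-10c arm against placebo with a score-based interval. At roughly ±21 to 24 points it will say little alone, but it shows how wide the uncertainty is.

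The cost is three restated intervals, a sentence in the SAP and a few table columns. Stated precision looks slightly worse. Enrolment, conduct and the descriptive status of the analysis are unchanged.
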